14.4 Subject Confidentiality

Subject confidentiality is strictly held in trust by the participating investigators, their staff, and the sponsor(s) and their agents. This confidentiality includes documentation, investigation data, subject's clinical information, and all other information generated during participation in the study. This material may be shown to other professional staff, used for educational purposes, or included in a scientific publication.

No information concerning the study or the data generated from the study will be released to any unauthorized third party without prior written approval of the sponsor and the subject.

The study monitor or other authorized representatives of the sponsor or governmental regulatory agencies may inspect all documents and records required to be maintained by the investigator, including but not limited to, medical records (office, clinic, or hospital) and pharmacy records for the subjects in this study. The clinical study site will permit access to such records.

14.5 PI Responsibility When Subject Withdraws or Is Discontinued

See Section 5.4

14.6 Referrals for HCV Treatment and Care

See Section 8.6.

15 Protocol Conduct

The protocol will be conducted in compliance with federal regulations, the principles of GCP and DMID standards, policies and procedures, including the following processes:

- Protocol registration, activation, and implementation;
- Informed consent, screening, and enrollment;
- Clinical and safety assessments;
- Safety monitoring and reporting;
- Data collection and documentation;
- Study follow-up and close-out;
- Unblinding of staff and subjects;
- Quality management;
- Protocol monitoring and compliance;
- Risk reduction counseling; and
- Specimen collection, processing, and analysis.

Any policies or procedures that vary from DMID standards or require additional instructions will be described in the study Manual of Procedures.

15.1 Subject Confidentiality

The investigators will maintain appropriate medical and research records for this trial, in compliance with ICH E6 GCP and regulatory and institutional requirements for the protection of confidentiality of subjects. The study protocol, documentation, data and all other information generated will be held in strict confidence. No information concerning the study or the data will be released to any unauthorized third party, without prior written approval of the sponsor. The principal investigators will obtain a Certificate of Confidentiality from NIH to further protect subjects' privacy.

15.2 Data Collection, Handling, Source Documents

Clinical research data will be collected as described in detail in Section 12.

Standard GCP will be followed to ensure accurate, reliable, and consistent data collection. Each participating site will maintain appropriate medical and research records for this trial, in compliance with ICH, GCP, regulatory, and institutional requirements for the protection of confidentiality of subjects.

15.3 Protocol Deviations

A protocol deviation is any noncompliance with the clinical trial protocol, Good Clinical Practice (GCP), or Manual of Procedures requirements. The noncompliance may be on the part of the subject, the investigator, or the study site staff. As a result of deviations, corrective actions are to be developed by the site and implemented promptly.

These practices are consistent with Good Clinical Practice:

- 4.5 Compliance with Protocol, sections 4.5.1, 4.5.2, and 4.5.3
- 5.1 Quality Assurance and Quality Control, section 5.1.1
- 5.20 Noncompliance, sections 5.20.1 and 5.20.2d

It is the responsibility of the site to use continuous vigilance to identify and report deviations within 5 working days of identification of the protocol deviation, or within 5 working days of the scheduled protocol-required activity. All deviations must be promptly reported to DMID, via The Emmes Corporation's IDES.

All deviations from the protocol must be addressed in study source documents. A completed copy of the DMID Protocol Deviation (PD) Form must be maintained in the Regulatory File. Protocol deviations must be submitted to the local IRB/IEC per their guidelines. The site PI/study staff is responsible for knowing and adhering to their IRB requirements.

15.4 Recruitment and Retention of Study Subjects

All subjects in this study will be adult subjects who are part of the cohort maintained by the study sites.

Recruitment and retention of young adult IDUs is challenging and requires an experienced culturally sensitive operational structure. The two original sites, Baltimore (MD) and San Francisco (CA) have been studying HCV in IDUs for over 10 years each and have developed successful accrual and follow up methods. Both established study sites have experience recruiting and retaining IDUs in prospective studies. An urban IDU cohort has been established in Baltimore under the supervision of [name] to create and maintain a cohort of persons at risk for acute HCV infection. This cohort will be continued and expanded. The infrastructure was originally established during parallel research on injection drug use that was funded by CDC and NIDA under the leadership of several principal investigators in the Bloomberg School of Public Health.⁸⁹⁻⁹³ At the San Francisco study site, prospective studies (under the collective name of The UFO Study) of young IDUs at risk of HCV and with acute HCV have been ongoing for 10 years.^{30,94} The study is directed and supervised by [name]; and currently has over

100 high risk HCV negative subjects in active follow up. The infrastructure is in existence, including trained personnel and a community-clinic based research site. [name] has recently initiated studies of HCV in young adult users in New Mexico where there is a significant HCV epidemic. The clinical study site and supporting laboratory infrastructure for conducting the study is located in Albuquerque, NM, proximal to the University of New Mexico Health Sciences Center.

The Co-Principal Investigators are leaders in the field of acute HCV research in the US and both have been studying HCV infection in injection drug users and other at-risk populations for over 10 years. They have extensive professional networks to which they refer research participants for care, including HCV treatment, vaccinations and primary care, drug treatment, mental health, housing, and other health resources. These investigators have extensive experience working with, and in referral and treatment of, HCV in injection drug users. They have working relationships with local providers who can evaluate, assess available resources for care, and treat HCV, including acute HCV, on a case-by-case basis. Both investigators are leaders in advocacy for access to HCV testing and treatment in injection drug users and other at-risk populations. In addition, [name] is an expert in the treatment of acute HCV infections and clinically manages therapy of HCV in IDUs.

We estimate that 2160 persons will need to be screened to enroll the target study population size of 540 (screening: enrollment ratio, 4:1); corresponding to screening 70 subjects/month and enrolling 17.5/month, corresponding to per site screening of 23 subjects/month and enrollment of 6/month. The San Francisco study had an average screening of 45/month and enrollment of 25/month during peak operations and operating study site three nights per week (screening for and enrolling only anti-HCV negative subjects). Baltimore has had similar accrual numbers. These estimates are based on a previous intervention study conducted with HCV negative IDUs (the DUIT Study⁹⁵). The vaccine trial will include resources for enhanced outreach to achieve the required 90% follow-up rate including: monthly visits, expanded clinic hours, and subject reimbursement, facilitated by a subject tracking database to ensure targeted rates.

All procedures for retention are described during informed consent. Retention is a coordinated activity involving several groups within the study team, including POWs, subject advocates, physicians, pharmacists, and counselors. Once a subject enrolls in this study, the study site will make every effort to retain him/her in follow-up to minimize possible bias associated with loss-to-follow-up. This study aims to achieve a minimum of 90% retention. Retention procedures and methods will include:

(1) Thorough explanation of the study visit schedule and procedural requirements during the informed consent process and re-emphasis at each study visit, and at study termination.

- (2) Compilation of detailed contact tracing and locator information at the study screening visits, and active review and updating of this information at each subsequent visit.
- (3) Use of mapping techniques to establish the location of subject residences and other locator venues.
- (4) Use of appropriate and timely visit reminder mechanisms.
- (5) Immediate and multi-targeted follow-up on missed visits.
- (6) Use of trained outreach workers to complete in-person contact with subjects at their homes and/or other community locations.
- (7) The study site will have a subject tracking database to facilitate visit scheduling and timely identification and follow-up on missed visits. The study team will generate weekly reports on the number and percentage of subjects completing the follow-up visits throughout the course of the study. Members of the Protocol Team will track retention rates closely and work with the study site as needed to take any required action to address below-target retention rates.

The key role for POWs in retention: Retention of IDU in prospective studies is extremely challenging and at all three sites, significant effort will be made to maximize retention. Every enrolled subject will be assigned to a POW, in accordance to a POW's geographical coverage during fieldwork. It is estimated that there will be approximately 50 subjects assigned to each POW. During enrollment, the counselor will notify the subject that he will be assigned a POW and the counselor will give the subject the POW's name. POWs will verify all the addresses of the subjects. Throughout the study, the recruitment coordinator or POW or their designee will remind his/her subjects by e-mail, text short message service (SMS) messaging, or by telephone of their upcoming appointments and invite them to any activities hosted at the study sites. Retention and follow-up rate will be assessed and reported periodically. Study coordinating meetings will include review and discussion of recruitment and retention, with case reviews and problem solving aimed at maximizing both.

15.5 Study Subject Reimbursement

Reimbursement of study subjects for attendance at study visits is at the discretion of each study site. Reimbursement should be comparable to the reimbursement offered for similar research in the local community, if possible. The study site is encouraged to confer with its local resources (including Community Advisory Boards, and other researchers) in deciding appropriate reimbursement.

The study informed consent submitted to the site IRB/IEC will state the plan for reimbursement (if any). The DMID relies upon local IRBs to determine whether the proposed plan for reimbursement meets ethical requirements in the local context. The

exact amounts may be modified during the course of the study in consideration of changes in costs such as bus fares, exchange rates, child care, or other factors that affect the ability of a subject to comply with study visit requirements. Reviewing IRBs must be made aware of the changes in reimbursement before they occur. Study subjects will not be charged for study injections, research clinic visits, research-related examinations, or research-related laboratory tests.

16 Publication Policy

All manuscripts resulting from this trial will be reviewed by representatives from the site(s), DMID and the product owner(s) (Okairos). Each institution will have thirty days to review the publication prior to submission.

Following completion of the study, the co-principal investigators will publish the results of this research in a scientific journal. The NIH Public Access Policy ensures the public has access to the published results of NIH funded research. It requires that all investigators submit or have submitted for them an electronic version of their final peer-reviewed journal manuscripts that arise from NIH funds to the digital archive of the National Library of Medicine's PubMed Central upon acceptance for publication. Further the policy stipulates that these papers must be accessible to the public on PubMed Central no later than 12 months after the official date of publication.

Refer to:

http://publicaccess.nih.gov

http://grants.nih.gov/grants /guide/notice-files/NOT-OD-08-033.html

Appendix A: Acceptable Ranges for Clinical Laboratory Evaluations at Screening

NOTE: When the site-specific laboratory normal range is available, if there is a discrepancy between the laboratory value in the Appendix and the site specific laboratory normal range, the site normal range will take precedence in eligibility determination.

HEMATOLOGY			
	Acceptable Range		
Hemoglobin F (g/dl)	11.5-15.0		
Hemoglobin M (g/dl)	12.5-17.0		
Platelet (K)	120-499		
WBCs (thou/mcl)	3.0-10.8		

CHEMISTRIES	
	Acceptable Range
Creatinine ^A	Within or below the normal range

^A Values lower than the normal range are not exclusionary.

ENZYMES	
	Acceptable Range
ALT (SGPT)	< 1.25 x ULN

URINALYSIS		
	Acceptable Range	
Glucose (mg/dl)	≤ 1+	
Protein (mg/dl)	≤ 1+	

Appendix B: Toxicity Table

ABBREVIATIONS: Abbreviations utilized in the Table:

ULN = Upper Limit of Normal	LLN = Lower Limit of Normal
Rx = Therapy	Req = Required
Mod = Moderate	IV = Intravenous
ADL = Activities of Daily Living	Dec = Decreased

NOTE: For any of the lab values listed below, if the Grade 1 value conflicts with the LLN value, the LLN value takes precedence and the event will not be considered a Grade 1 Adverse Event.

When the site-specific laboratory normal range is available, if there is a discrepancy between the laboratory value in the Appendix and the site specific laboratory normal range, the site normal range will take precedence in determining Grade 1 Adverse Events.

ESTIMATING SEVERITY GRADE

For abnormalities NOT found elsewhere in the Toxicity Tables use the scale below to estimate grade of severity:

- GRADE 1: **Mild** (events require minimal or no treatment and do not interfere with the subject's daily activities.)
- GRADE 2: **Moderate** (events result in a low level of inconvenience or concern with the therapeutic measures. Moderate events may cause some interference with functioning)
- GRADE 3: **Severe** (events interrupt a subject's usual daily activity and may require systemic drug therapy or other treatment. Severe events are usually incapacitating.)
- GRADE 4: Life-threatening (Any adverse drug experience that places the subject or subject, in the view of the investigator, at immediate risk of death from the reaction as it occurred, i.e., it does not include a reaction that had it occurred in a more severe form, might have caused death).

SERIOUS OR LIFE-THREATENING AEs

ANY clinical event deemed by the clinician to be serious or life-threatening should be considered a grade 4 event. Clinical events considered to be serious or life-threatening include, but are not limited to: seizures, coma, tetany, diabetic ketoacidosis, disseminated intravascular coagulation, diffuse petechiae, paralysis, acute psychosis, severe depression.

HEMATOLOGY				
	Grade 1	Grade 2	Grade 3	Grade 4
Hemoglobin (g/dl)				
Male:	11.0-12.4	9.6-10.9	8.3-9.5	<8.3
Female:	9.6-10.8	8.4-9.5	7.2-8.3	<7.2
Platelets (per cumm)	84,500-117,000	65,000-84,499	25,000-64,999	< 25,000
WBCs (thou/mcl)				
Lower Limit	2.5-2.9	1.9-2.4	1.0-1.8	<1.0
Upper Limit	11.9-15.1	15.2-21.6	21.7-25.0	>25

CHEMISTRIES	CHEMISTRIES				
	Grade 1	Grade 2	Grade 3	Grade 4	
Hypokalemia	3.0 - 3.4 mEq/L	2.5 - 2.9 mEq/L	2.0 - 2.4 mEq/L or intensive replacement therapy or hospitalization required	<2.0 mEq/L or abnormal potassium with paresis, ileus or life-threatening arrhythmia	
Hyperkalemia	5.6 - 6.0 mEq/L	6.1 - 6.5 mEq/L	6.6 - 7.0 mEq/l	>7.0 mEq/L or abnormal potassium with life-threatening arrhythmia	
Hyperglycemia (nonfasting and no prior diabetes) NOTE: (normal range for Glucose, Random, Serum is 60-199 mg/dL for one site laboratory)	200 - 274 mg/dL	275 - 349 mg/dL	350 - 499 mg/dL	>500 mg/dL or abnormal glucose with ketoacidosis or seizures	
Hypophosphatemia	2.0 - 2.4 mg/dL	1.5 -1.9 mg/dL or replacement Rx required	1.0 -1.4 mg/dL intensive therapy or hospitalization required	< 1.0 mg/dL or abnormal phosphate with life-threatening arrhythmia	
Hyperbilirubinemia (when accompanied by any increase in other liver function test)	1.1 - <1.25 x ULN	1.25 - <1.5 x ULN	1.5 – 1.75 x ULN	>1.75 x ULN	
Hyperbilirubinemia (when other liver function are in the normal range)	1.1 - <1.5 x ULN	1.5 - <2.0 x ULN	2.0 – 3.0 x ULN	>3.0 x ULN	

CHEMISTRIES cont.				
	Grade 1	Grade 2	Grade 3	Grade 4
BUN	1.25 - 2.5 x ULN	2.6 - 5 x ULN	5.1 - 10 x ULN	>10 x ULN
Creatinine*	1.2 - 1.5 x ULN	>1.5- 2 x ULN	>2 x ULN	Dialysis required
СРК	2.0-3.4 x ULN	3-5.9 x ULN	6-9.9 x ULN	> 10 x ULN

* Use age and gender appropriate values

ENZYMES				
	Grade 1	Grade 2	Grade 3	Grade 4
AST (SGOT)	>1.25 -2.5 x ULN	>2.5 – 4 x ULN	>4 -8 x ULN	>8 x ULN
ALT (SGPT)	>1.25 - 2.5 x ULN	>2.5 – 4 x ULN	>4 -8 x ULN	> 8 xULN
LDH	>1.25 - 2.5 x ULN	>2.5 – 4 x ULN	>4-8xULN	> 8 x ULN
GGT	1.1 - <2.0 x ULN	2.0 – <3.0 x ULN	3.0 – 8.0 x ULN	>8 x ULN
Alkaline Phosphatase	1.1 - <2.0 x ULN	2.0 – <3.0 x ULN	3.0 – 8.0 x ULN	>8 x ULN
Amylase	1.1 - 1.5 x ULN	1.6 - 2.0 x ULN	2.1 - 5.0 x ULN	>5.0 x ULN
Lipase	1.1 - 1.5 x ULN	1.6 - 2.0 x ULN	2.1 - 5.0 x ULN	>5.0 x ULN

URINALYSIS				
	Grade 1	Grade 2	Grade 3	Grade 4
Proteinuria	1+ or 200 mg – 1 gm loss/day	2-3 + or 1-2 gm loss/day	4+ or 2-3.5 gm loss/day	Nephritic syndrome or >3.5 gm loss/day
Hematuria	Microscopic only <10 rbc/hpf	Gross, no clots >10rbc/hpf	Gross, with or without clots, OR red blood cell casts	Obstructive or required transfusion
Glucose	1+	2+	3+	4+

CARDIOVASCULAR				
	Grade 1	Grade 2	Grade 3	Grade 4
Cardiac Rhythm	Not defined	asymptomatic, transient signs, no Rx required	recurrent/ persistent; symptomatic Rx required	unstable dysrhythmia; hospitalization and treatment required

CARDIOVASC	CARDIOVASCULAR cont.				
	Grade 1	Grade 2	Grade 3	Grade 4	
Hypertension	Asymptomatic transient (<24 hrs) increase >20 mmHg in diastolic or to >140/90 and ≤150/95 mmHg; no treatment	recurrent or persistent (>24 hrs) or symptomatic increase >20 mmHg in diastolic or to >151/96 and ≤155/100 mmHg; monotherapy may be indicated	requiring more than one drug or more intensive therapy than previously or to >155/100 mmHg	Life-threatening consequences (e.g. hypertensive crisis)	
Hypotension	non applicable	Symptomatic corrected with oral fluids	Symptomatic IV fluids indicated	Shock–requiring use of vasopressors or mechanical assistance to maintain blood pressure	
Pericarditis	minimal effusion	mild/moderate asymptomatic effusion, no treatment	symptomatic effusion; pain; EKG changes	tamponade; pericardiocentesis or surgery required	
Hemorrhage, Blood Loss	microscopic/occult	mild, no transfusion	gross blood loss; 1-2 units transfused	massive blood loss; >3 units transfused	

SKIN				
	Grade 1	Grade 2	Grade 3	Grade 4
Mucocutaneous	erythema; pruritus	diffuse, maculo papular rash, dry desquamation	vesiculation or moist desquamation or ulceration	exfoliative dermatitis, mucous membrane involvement or erythema, multiforme or suspected Stevens- Johnson or necrosis requiring surgery
Induration	<25mm	25 - 50 mm	>50mm	
Erythema	<25mm	25 - 50 mm	>50mm	
Edema	<25mm	25 - 50 mm	>50mm	
Rash at Injection Site	<25mm	25 - 50 mm	>50mm	
Regional lymphadenopathy	Soft/spongy	Firm	Hard	

SKIN cont.				
	Grade 1	Grade 2	Grade 3	Grade 4
Pruritus	slight itching at injection site	moderate itching at injection extremity	itching over entire body	

SYSTEMIC	SYSTEMIC												
	Grade 1	Grade 2	Grade 3	Grade 4									
Allergic Reaction	pruritus without rash	localized urticaria	generalized urticaria; angioedema	Anaphylaxis									
Fever: oral	38.0 – 39.0 °C 100.4 F - 102.2 °F	>39.0 – 40.0 °C 102.3F - 104.0 °F	>40.0 °C >104.0 °F										

MUSCULOS	MUSCULOSKELETAL											
	Grade 1	Grade 2	Grade 3	Grade 4								
Arthritis	mild pain with inflammation, erythema or joint swelling – but not interfering with function	moderate pain with inflammation, erythema or joint swelling – interfering with function, but not with activities of daily living	severe pain with inflammation, erythema or joint swelling – and interfering with activities of daily living	permanent and/or disabling joint destruction								

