9.2 Definitions

Adverse Event (AE)

An AE is any untoward medical occurrence in a clinical investigation subject who has received a study intervention and that does not necessarily have to have a causal relationship with the study product. An AE can, therefore, be any unfavorable and unintended sign (including an abnormal laboratory finding, for example), symptom, or disease temporally associated with the use of the study product, whether or not considered related to the study product.

Unexpected

An unexpected AE is an adverse reaction, the nature or severity of which is not consistent with the applicable product information (e.g., investigator's brochure [IB] for an unapproved investigational medicinal product). Unexpected refers to an experience that has not been previously observed. This includes events that are more serious than expected or occur more frequently than expected.

Expected

Any adverse experience, the nature, severity or frequency of which is consistent with the current IB; or with the risk information described in the investigational plan or protocol or consent form.

Serious Adverse Event (SAE)

An adverse event or suspected adverse reaction is considered "serious" if, in the view of either the investigator or sponsor, it results in any of the following outcomes:

- Death,
- A life-threatening adverse event*,
- Inpatient hospitalization or prolongation of existing hospitalization,
- A persistent or significant incapacity or substantial disruption of the ability to conduct normal life functions, or
- A congenital anomaly/birth defect.
- Important medical events that may not result in death, be life-threatening, or require hospitalizations may be considered serious when, based upon appropriate medical judgment, they may jeopardize the subject and may require medical or surgical intervention to prevent one of the outcomes listed in this definition. Examples of such medical events include allergic bronchospasm requiring intensive treatment in an emergency room or at home, blood dyscrasias or convulsions that do not result in subject hospitalization, or the development of drug dependency or drug abuse.
- * Life-threatening adverse event. An adverse event is considered "life-threatening" if, in the view of either the investigator or sponsor, its occurrence places the subject or subject at immediate risk of death. It does not include an adverse event, had it occurred in a more severe form, might have caused death.

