9.4.1 Assessment of Seriousness

Event seriousness will be determined according to the protocol definition of an SAE (Section 9.2).

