9.4.2 Assessment of Severity

Event severity will be graded according to parameters shown in Appendix B or if not, noted in the tables using the definitions below:

- 1 = Mild (awareness of a symptom but the symptom is easily tolerated; the symptom requires minimal or no treatment)
- 2 = Moderate (discomfort enough to cause interference with usual activity)
- 3 = Severe (incapacitating; unable to perform usual activities; requires absenteeism/bed rest)
- 4 = Life-threatening
- 5 = Death

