9.3.2. Unsolicited Adverse Events

Adverse events will be collected through day 90. At visits following Day 90, only SAE's will be collected. Adverse events will be graded on a scale of 0 (none), 1 (mild), 2 (moderate), 3 (severe), 4 (life threatening), and 5 (death).

Adverse events will be coded to a Medical Dictionary for Regulatory Activities Terminology (MedDRA) version 20.1 or later. Verbatim description, the MedDRA System Organ Class, and Preferred Term for all adverse events will be contained in the subject data listings.

The proportion of subjects reporting at least one unsolicited adverse event will be summarized by dose and over all doses, MedDRA® system organ class (SOC) and preferred term (PT) for all subjects and each actual treatment group. Denominators for percentages are the number of subjects who received the dose being summarized. A 95% Blaker CI will be presented for each SOC and PT. (Table 58, Table 59, Table 60)

Adverse events by subject will be presented in Listing 11.

The following summaries for unsolicited adverse events will be presented by SOC, PT, dose and treatment group:

- Number and percentage of subjects by dose, HCV Infection Status, maximum severity and maximum relationship to study product including Frequency (Event level) of events for all subjects and by actual treatment received ([Table 61](#), [Table 62](#), [Table 63](#), [Table 64](#), [Table 65](#), [Table 66](#));
- Number and percentage of subjects by dose, HCV Infection Status, maximum severity and maximum relationship to study product including Frequency (Event level) of events for all subjects and by actual treatment received ([Table 67](#), [Table 68](#), [Table 69](#));
- Subject incidence and total frequency of adverse events over time (Days 1-8, Days 8-55, Days 56-63, Days 64-90) ([Table 70](#), [Table 71](#), [Table 72](#));
- Subject listing of non-serious adverse events of moderate or greater severity ([Table 73](#));
- Bar chart of total frequency of adverse events by severity and SOC ([Figure 27](#));
- Bar chart of subject incidence of adverse events by severity and SOC ([Figure 28](#));
- Bar chart of total frequency of adverse events by relationship to study product and SOC ([Figure 29](#));
- Bar chart of subject incidence of adverse events by relationship to study product and SOC ([Figure 30](#));

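### Appendix B grades any serious event as Grade 4, in conflict with the plan's separate severity scale, and the by-severity adverse event tables have no row for Grade 5

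*Protocol*

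**What the plan says.** Appendix B, under its heading on serious or life-threatening adverse events, says that "ANY clinical event deemed by the clinician to be serious or life-threatening should be considered a grade 4 event". Just above, in the scale for abnormalities not listed elsewhere in the tables, it reads "GRADE 4: Life-threatening (Any adverse drug experience that places the subject or subject, in the view of the investigator, at immediate risk of death". Appendix B has no Grade 5.

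Protocol 9.2 gives several criteria for a serious event that do not require immediate risk of death. One is "Inpatient hospitalization or prolongation of existing hospitalization"; others are incapacity, congenital anomaly and important medical events. Protocol 9.4.1 ties seriousness to that list: "Event seriousness will be determined according to the protocol definition of an SAE (Section 9.2". Protocol 9.4.2 then treats severity as a separate matter: "Event severity will be graded according to parameters shown in Appendix B or if not, noted in the tables using the definitions below". The definitions that follow run from 1 to 5, with 4 for life-threatening and 5 for death.

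SAP 4.5 also names Appendix B first for unsolicited events, with the 9.4.2 definitions for events graded differently. SAP 9.3.2 states that "Adverse events will be graded on a scale of 0 (none), 1 (mild), 2 (moderate), 3 (severe), 4 (life threatening), and 5 (death". SAP 9.4 summarizes SAEs by maximum severity in Tables 77-82.

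**The concern.** Seriousness concerns outcome and regulatory reporting; severity concerns intensity. The protocol separates them in 9.4.1 and 9.4.2, but the Appendix B sentence makes the first determine the second. It sits in the source that graders are told to use first.

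What is at stake is how SAE and unsolicited event severity is displayed by arm and by site. Safety is a primary objective, and Tables 61-69 and 77-82 are the by-severity summaries of these events. If some graders follow the Appendix B sentence and others the 1-5 scale, the Life Threatening row mixes events at immediate risk of death with events that merely met a seriousness criterion.

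The missing Grade 5 row is a second, independent problem. It would remain even if Appendix B were corrected.

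**Working it through.** The plan gives no figure to reproduce, so the check sets the texts side by side.

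| Source | Grades | What Grade 4 means | Grade for death |
|---|---|---|---|
| Appendix B, general scale | 1-4 | Immediate risk of death | None |
| Appendix B, sentence on serious events | n/a | Any clinical event deemed serious or life-threatening | None; 4 by default |
| Protocol 9.4.2 | 1-5 | Life-threatening | 5 |
| SAP 9.3.2 | 0-5 | Life-threatening | 5 |
| Shells, Tables 61-69 and 77-82 | Mild, Moderate, Severe, Life Threatening, plus Any Severity | Life Threatening | No row |

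**Conflict inside Appendix B.** Grade 3 hypokalemia is "2.0 - 2.4 mEq/L or intensive replacement therapy or hospitalization required", and the hypophosphatemia row likewise places a need for hospitalization at Grade 3. Inpatient hospitalization is a seriousness criterion in 9.2, so an admission for either is Grade 3 by its row and Grade 4 if the sentence on serious events is applied. The cardiac rhythm row does mention hospitalization at Grade 4, but together with an unstable dysrhythmia. The rows therefore do not treat hospitalization alone as Grade 4.

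**Worked case 1: a moderate infection admitted overnight, with no immediate risk of death.**
- By 9.2 it is serious.
- By the Appendix B sentence it is Grade 4 and goes in the Life Threatening row.
- By 9.4.2, if it only interferes with usual activity, it is Grade 2 and goes in the Moderate row.

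Grading is done by onsite investigators (Protocol 9.4) at three sites. Tables 67-69 show severity by site, so different readings of the text could look like a site difference.

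**Worked case 2: a fatal SAE.**
- By the Appendix B sentence it is Grade 4 and has a row.
- By 9.4.2 and SAP 9.3.2 it is Grade 5 and has none.

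The shells count a subject once per preferred term, at the highest severity. For a given preferred term, let n be the number of subjects under Any Severity and d the number whose highest grade is 5. Then

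Mild + Moderate + Severe + Life Threatening = n - d.

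The rows fall short of the total by exactly the fatal cases.

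**Extent.** Tables 61-69 are 9 tables and Tables 77-82 are 6, so 9 + 6 = 15 tables share the four severity rows. Shells are given for Tables 61, 62, 67, 77 and 78; the rest reuse their format. Figures 27-28 also display severity, but their mock-ups are not visible, so their categories cannot be checked.

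**The case against.** The strongest reply is that the Appendix B sentence was not meant literally. It speaks of events the clinician deems serious without citing 9.2, and its examples are mostly grave states such as coma and paralysis. The general Grade 4 definition beside it requires immediate risk of death. SAP 4.5 does not make Appendix B the sole scale. The SAE shells have Mild, Moderate and Severe rows, so the SAP expects SAEs below Grade 4.

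This defeats one tempting inference: that every SAE will be reported as life-threatening and the three lower rows will be empty. That follows only if every grader applies the sentence literally, which the documents do not establish. It does not remove the conflict, because the sentence covers any such event and graders reach it before the 1-5 scale.

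A reader might also infer that fatal events vanish from the report. They do not: they count under Any Severity and appear in the SAE listing (Table 83) and the death listing (Table 84). Nor can both extremes hold for the same event. All SAEs at Grade 4 is the literal Appendix B reading, under which a death does have a row; a death without a row arises only under 9.4.2 and SAP 9.3.2.

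It is also fair that the effect is descriptive. Table 76 compares proportions with vaccine-related SAEs regardless of grade, and solicited events use their own 0-3 scale. Table 83 shows the reason for seriousness, severity and outcome separately for each SAE, so a careful reader could detect misgrading. Those points limit the harm but do not correct the summary tables.

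**Conclusion.** The plan is wrong as written on two counts. First, the Appendix B rule contradicts Appendix B's own Grade 4 definition, two of its Grade 3 rows, Protocol 9.4.1 and 9.4.2, and SAP 9.3.2. The severity recorded for a serious, non-life-threatening event therefore depends on which text is followed. Second, the shells for 15 tables omit a grade that the protocol and SAP both define.

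The first conclusion assumes only that some SAEs are not life-threatening, which the 9.2 criteria allow. The second matters only if a fatal event occurs and is graded 5.

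The size cannot be stated. It would be tempting to multiply an assumed SAE proportion by the 540 subjects, but the documents give no such proportion, and Protocol 11.4.2 expects the number of SAEs to be small. Such a product would also count SAEs, not misgraded ones. With few SAEs, each misgraded event shifts the displayed profile more. The correction should be made before database lock; it does not bear on the primary SAE test.

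**What to change.** 1. Reconcile Appendix B with Protocol 9.4.2 so that a single severity scale, separate from seriousness, applies. The heading, the sentence and the example list all pair serious with life-threatening, so editing the sentence alone would leave the conflict in place. SAP 4.5 and 9.3.2 should cite the same scale.
2. Add a Grade 5 (Death) row to the shells for Tables 61-69 and 77-82, and check that Figures 27-28 carry the same categories.
3. Before lock, and with treatment codes still masked, query each SAE graded 4 that does not meet the life-threatening definition, and record any change of grade.

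The cost is a clarification to the protocol, one added row in the table shells, and a data query on SAE grades. No new data collection is needed, and no planned test changes.
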